10.5 Serious Adverse Events

Any adverse Event that meets any of the following criteria: (1) results in death; (2) is life-threatening (i.e. places a participant at immediate risk of death from the event as it occurred); (3) requires inpatient hospitalization or prolongation of existing hospitalization; (4) results in a persistent or significant disability/incapacity; (5) results in a congenital anomaly/birth defect; OR (6) any other adverse event that, based upon appropriate medical judgment, may jeopardize the participant's health and may require medical or surgical intervention to prevent one of the other outcomes listed in this definition (e.g. allergic bronchospasm requiring intensive treatment in the emergency room or at home).

Information about all serious adverse events, whether volunteered by the subject, discovered by investigator questioning, or detected through physical examination, laboratory test or other means, will be collected and recorded on the Serious Adverse Event eCRF.

For this study, all SAEs occurring from the time of drug administration to 30 days post-study completion visit will be captured on the SAE eCRF. As the Month 36 Visit is a Phone Call Visit, review of subjects' medical records is required, in order to evaluate any SAEs within 30 days post-study completion visit. Unless exempted as described below, all SAEs, whether or not deemed drug-related, must be reported by the investigator or qualified designee within 1

business day of first becoming aware of the event. The investigator/qualified designee will enter the required information regarding the SAE into the appropriate module of the IBM Clinical Development, which will automatically result in distribution of the information to the Duke Clinical Research Institute Medical Monitor and Clinical Operations team, and the Network Management Core (NEMO). If IBM Clinical Development is temporarily unavailable, the event, including the investigator-determined causality to study drug, should be reported via a paper back-up SAE form to the DCRI Medical Monitor and Clinical Operations team, and the NEMO. Upon return of the availability of EDC system, the SAE information must be entered into the eCRF.

Follow-up: When additional relevant information becomes available, the Investigator will record follow-up information according to the same process used for reporting the initial event as described above. The Investigator will follow all reportable events until resolution, stabilization or the event is otherwise explained.

Investigators are also responsible for promptly reporting SAEs to their reviewing IRB/EC in accordance with local requirements.

The DCRI Medical Monitor and Clinical Operations team, and NEMO will follow all SAEs until resolution, stabilization, until otherwise explained or until the last subject completes the final follow-up, whichever occurs first. The DCRI Medical Monitor and Clinical Operations team will report all SAEs to the CleanUP-IPF trial team within 1-2 business day(s) of receipt and notify the Data Safety Monitoring Board (DSMB) chair monthly. If no events have occurred, the DCRI Clinical Operations team will notify the NEMO, and NEMO will notify the DSMB chair as such.

An independent DSMB will review composite data at regular intervals throughout the study. The DSMB will be empowered to stop the study for evidence of efficacy or harm.

Events Relatedness refers to the extent to which an adverse event is considered to be related to the intervention or study procedures. An adverse event is considered related if there is a reasonable possibility that the event may have been caused by the procedure. The following definitions apply to relatedness, per the Pulmonary Trials Cooperative's Manual of Operations:

- 1) Unrelated: adverse event is clearly due to extraneous causes (e.g., underlying disease, environment)
- 2) Unlikely: (adverse event **must meet 2** of the following criteria):
 - Does not have temporal relationship to intervention
 - Could readily have been produced by the participant's clinical state
 - Could have been due to environmental or other interventions
 - Does not follow known pattern of response to intervention
 - Does not reappear or worsen with reintroduction of intervention
- 3) Possible: (adverse event **must meet 2** of the following criteria):

- Has a reasonable temporal relationship to intervention
- Could not readily have been produced by the participant's clinical state
- Could not readily have been due to environmental or other interventions
- Follows a known pattern of response to intervention

4) Probable: (adverse event **must meet 3** of the following criteria):

- Has a reasonable temporal relationship to intervention
- Could not readily have been produced by the participant's clinical state or have been due to environmental or other interventions
- Follows a known pattern of response to intervention
- Disappears or decreases with reduction in dose or cessation of intervention

5) Definite: (adverse event **must meet 4** of the following criteria):

- Has a reasonable temporal relationship to intervention
- Could not readily have been produced by the participant's clinical state or have been due to environmental or other interventions
- Follows a known pattern of response to intervention
- Disappears or decreases with reduction in dose or cessation of intervention and recurs with re-exposure

10.6 Pregnancy

Pregnancy occurring during a clinical investigation, although not considered a serious adverse event, must be reported to DCRI within the same timelines as a SAEs. The pregnancy will be recorded on the appropriate paper pregnancy tracking form. The pregnancy will be followed until final outcome. Any associated SAEs that occur to the mother or fetus/child will be recorded in the SAE eCRF, within IBM Clinical Development.

All pre-menopausal female participants will have a urine sample collected at their screening/baseline visit, and a urine dipstick pregnancy test will be completed.

In an effort to prevent pregnancies from occurring during a subject's participation in the study, women of child-bearing potential must use two acceptable methods of contraception at the same time unless the subject has had a surgical sterilization, in which case no additional contraception is required. Medically acceptable contraceptives include: (1) documented surgical sterilization (such as a hysterectomy, tubal ligation), (2) barrier methods (such as a condom or diaphragm) used with a spermicide, (3) hormonal contraception (combination oral contraceptives, transdermal patch, injectables, implantables, or vaginal ring) or (4) an intrauterine device (IUD) or intrauterine system (IUS). Abstinence is not an acceptable form of contraception in this study.

Male participants must also agree to take all necessary measures to avoid causing pregnancy in their sexual partners during the study. Medically acceptable contraceptives include: (1) surgical

sterilization (such as a vasectomy), or (2) a condom used with a spermicidal. Contraceptive measures such as Plan B (™), sold for emergency use after unprotected sex, are not acceptable methods for routine use.

11. STATISTICAL CONSIDERATIONS

11.1 Overview

Means, standard deviations, medians, 25th and 75th percentiles will be presented for continuous variables; the number and frequency of patients in each category will be presented for nominal variables. Statistical tests with a two-sided p value <0.05 will be considered statistically significant, unless otherwise stated. Analyses will be performed using SAS software (SAS Institute, Inc., Cary, NC).

11.2 Analysis of Primary Endpoint

Detailed description of the plan for statistical analysis of each endpoint will be detailed in a Statistical Analysis Plan. The primary analysis will be based on intention to treat. Crossovers will be tracked and we will have an alternate analysis cohort based on these data. Subjects receiving lung transplantation will be censored for all endpoints at the time of transplantation.

The statistical comparison of the two randomized arms with respect to the primary endpoint will be a time-to-event analysis, and therefore will be based on the time from randomization to first non-elective, respiratory hospitalization or death from any cause. The Cox proportional hazards regression model will be the primary tool to analyze and assess outcome differences between the two treatment arms. The Cox model will include an indicator variable for treatment group, age, sex, baseline DLCO (pp), baseline FVC (pp), use of NAC at enrollment, and choice of antimicrobial agent prior to randomization. Hazard ratios and 95% confidence intervals will summarize the differences between treatment arms.

For the primary analysis, subjects without any respiratory hospitalization or death event at the time of analysis will be censored at their last visit or lung transplantation. The censoring mechanism is assumed to be non-informative. Supportive analyses will be performed to assess the impact of a potential informative censoring.

11.3 Sample Size Justification

Based on prior work from the study team using IPFnet data, it is anticipated that the event rate in the placebo arm will be highly dependent on the proportion of patients enrolled at the different GAP scores. Given the availability of two FDA-approved drugs for IPF, it is our belief that the study population will be heavily weighted toward GAP scores of 3. In **Table 1**, the statistical power is determined for designs enrolling 500 patients with placebo group events rates varying from 24% to 36% and (12-month) treatment effects varying from 30% to 35%. In

general, the proposed design provides adequate power expect when the 12-month standard-of-care group event rate is 24% and the reduction in events is less than 30%.

Table 1. Statistical Power Assuming a Sample Size of 500 Randomized Patients

Standard-of-care event rate*	Antimicrobial therapy strategy event rate*	One-year Event Rate Reduction	Power
24%	16.8%	30%	78%
30%	21.0%	30%	87%
36%	25.2%	30%	93%
24%	16.0%	33.3%	86%
30%	20.0%	33.3%	93%
36%	24.0%	33.3%	97%
24%	15.6%	35%	89%
30%	19.5%	35%	95%
36%	23.4%	35%	98%

*12-month event rates. Calculations assume a 2-sided Type-I error rate of 0.05. The minimum follow-up is planned to be 12 months and the maximum follow-up is 42 months. Drop-out rates are assumed to be approximately 2% per year. Power calculations were based on a log-rank test with assumed event rates were exponentially distributed. Calculations were computing using nQuery 7.0 software.

We plan to enroll 500 patients over a 30 month window with a minimum of 12 months of follow-up on all patients. **Table 2** shows the required number of endpoint events to have 80% to 90% power with hazard ratios varying from 0.50 to 0.75.

Table 2. Required number of events

	HR=0.50	HR=0.55	HR=0.60	HR=0.65	HR=0.70	HR=0.75
80% power	65	88	120	169	247	379
85% power	75	100	138	194	282	434
90% power	87	118	161	226	330	508

Calculations performed using nQuery 7.0 and assume a 0.05 type I error rate (two-sided) with 1:1 randomization.

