5.1 Randomization

All patients will be randomized using the study electronic data capture (EDC) system. Patients will be randomized to treatment in a 1:1 allocation ratio using a simple randomization scheme.

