8. FOLLOW UP EVALUATIONS

All study participants will continue to be followed on a usual care basis. Refer to the schedule of assessments for more details. Study participants will be followed for up to a maximum of 36 months. It is anticipated that the overall study will end once the final enrolled patient completes their 12-month visit. Subjects randomized to antimicrobial therapy will remain on the assigned therapy until the end of the study or their 36-month study visit. Study participants are encouraged to contact their treating pulmonologist regarding their use of anti-microbial therapy after their study participation has ended. At the completion of the 36-month phone contact data collection will cease. To gain a better understanding of the long-term consequences of treatment, patients may be contacted up to 5 years after the end of their study participation. The primary analyses will be based on data collected until the end of the active treatment portion of the study.

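### Protocol 11.3: the adequate-power sentence omits the one Table 1 row below 80% and is too narrow below 30% reductions; its 42-month follow-up conflicts with the 36-month cap, at a cost of about half a point of power

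*Protocol*

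**What the plan says.** Protocol 11.3 says that "the statistical power is determined for designs enrolling 500 patients", with standard-of-care 12-month event rates of 24%, 30% and 36% and "treatment effects varying from 30% to 35" per cent. It then sums up: power is adequate in general, except when the 12-month standard-of-care "group event rate is 24% and the reduction in events is less than 30" per cent (the protocol prints *expect* for *except*). Table 1 follows with nine rows. The first, 24% against 16.8% (a 30% reduction), shows 78% power. The other eight show 86% to 98%. No row has a reduction below 30%.

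The Table 1 footnote gives the inputs: "Calculations assume a 2-sided Type-I error rate of 0.05", a log-rank test with exponential event times, about 2% drop-out per year, at least 12 months of follow-up, and "the maximum follow-up is 42 months". The 42 months is the 30-month enrolment window plus the 12-month minimum. Table 2, in the same section, lists the events needed for 80%, 85% and 90% power.

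Protocol section 8 says "Study participants will be followed for up to a maximum of 36 months". Section 8.10 ends study data collection at the 36-month phone contact, and Appendix A schedules no later visit.

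**The concern.** Two statements in the power section do not agree with the rest of the protocol.

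The first is the exception. It is limited to reductions strictly under 30% at a 24% control rate. The only tabulated case below 80% sits at exactly 30%, so the sentence counts it as adequate. By naming only the 24% rate, the sentence also implies that reductions under 30% are adequately powered at control rates of 30% and 36%. Table 1 gives no figures for that.

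The second is the follow-up. Patients enrolled in the first six months of accrual would need more than 36 months of follow-up to match the footnote, and sections 8 and 8.10 do not provide it.

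What is at stake is the public description of what the trial could detect. The letter attached to the SAP addendum records early termination for futility, so readers may return to this sentence to judge which effects the design was able to find.

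**Working it through.** **Inputs.** From Protocol 11.3: 500 patients, two-sided alpha 0.05, log-rank test, exponential events, drop-out 2% per year, 30 months of accrual, 12 months minimum follow-up. From Protocol 5.1: 1:1 allocation, so 250 per arm. Assumptions: uniform accrual, and 80% as the benchmark for *adequate*.

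**Formulas** (time in years)
- Hazard from a 12-month rate p: λ = −ln(1 − p). Drop-out hazard: δ = −ln(0.98) = 0.0202.
- Probability of an observed event with potential follow-up t: λ/(λ + δ) × [1 − exp(−(λ + δ)t)], averaged over t uniform from 1 to 3.5. With the cap, t is replaced by min(t, 3).
- Expected events: D = 250 × (P1 + P2).
- Power (Freedman): Φ[√D × (1 − HR)/(1 + HR) − 1.96].

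**Step 1: reproduce the printed 78%.** For 24% against 16.8%, λ1 = 0.2744, λ2 = 0.1839 and HR = 0.670. With 42 months, P1 = 0.4405 and P2 = 0.3256, so D = 250 × 0.7661 = 191.5. The argument of Φ is 13.84 × 0.330/1.670 − 1.96 = 0.77, which gives 78.0%. The Lachin-Foulkes form gives 78.2% and the Schoenfeld form 79.1%. All three are below 80%. All nine rows reproduce within 1 point with Freedman and within 2 points with the other two, so Table 1 is right for its stated inputs.

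**Step 2: cap follow-up at 36 months.** The cap touches only patients enrolled in the first 6 of 30 months (20%). For the same row, P1 = 0.4351 and P2 = 0.3208, so D = 189.0 and power is 77.5%. All rows (Freedman):

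| Control rate | Reduction | Printed | 42 months | 36 months | Events lost |
|---|---|---|---|---|---|
| 24% | 30% | 78% | 78.0% | 77.5% | 2.5 |
| 30% | 30% | 87% | 87.2% | 86.8% | 2.7 |
| 36% | 30% | 93% | 93.2% | 92.9% | 2.6 |
| 24% | 33.3% | 86% | 86.4% | 86.0% | 2.5 |
| 30% | 33.3% | 93% | 93.4% | 93.1% | 2.7 |
| 36% | 33.3% | 97% | 97.1% | 96.9% | 2.6 |
| 24% | 35% | 89% | 89.7% | 89.3% | 2.5 |
| 30% | 35% | 95% | 95.4% | 95.2% | 2.7 |
| 36% | 35% | 98% | 98.2% | 98.1% | 2.6 |

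The largest loss in the table is about 0.5 points. At the untabulated 24% rate with a 25% reduction it is about 0.6 (61.5% to 60.9%).

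**Step 3: find where power crosses 80%.** Solving for the reduction that gives exactly 80% power:

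| Control rate | 36 months, Freedman | Range over Freedman and Schoenfeld, with and without the cap |
|---|---|---|
| 24% | 30.9% | 30.3% to 30.9% |
| 30% | 27.4% | 27.0% to 27.4% |
| 36% | 24.7% | 24.4% to 24.7% |

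At a 30% control rate with the cap, power is 84.4% for a 29% reduction, 81.7% for 28% and 72.0% for 25%. For a 25% reduction it is 60.9% at a 24% rate and 81.0% at a 36% rate.

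**The case against.** The strongest reply is that this is a slip of phrasing. The sentence is hedged as a general statement, 80% is never set as the threshold for Table 1, and the miss is two points. The 78% is printed directly under the sentence, so a careful reader sees it. Among tabulated cases, all six rows at control rates of 30% and 36% show 87% or more, so the sentence fails for one row of nine. All of that stands, and it is why the point is minor. It does not make the exception correct: as worded, it covers no tabulated row and leaves out the only weak one.

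Three stronger readings are tempting, and the documents do not support them.
- A reader might infer that every reduction below 30% is underpowered at a 30% control rate. It is not: power stays above 80% down to about 27%.
- A reader might infer that Table 1 itself refutes the sentence for reductions below 30%. It has no such rows; that part rests on recalculation outside the range the protocol examined.
- A reader might infer that the 36-month cap leaves the trial materially underpowered. It costs about half a point.

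On follow-up, section 8 allows contact for up to 5 years after participation ends. That does not rescue the 42 months, because the same section bases the primary analyses on data from the active treatment portion.

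**Conclusion.** The point holds as a minor correction with two parts.

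The adequacy sentence is wrong at its boundary. A 30% reduction at a 24% control rate has 78% power by the protocol's own table, and about 31% is needed to reach 80%. It is also too narrow, because the 30% control rate falls below 80% for reductions under about 27%. Both statements depend on reading *adequate* as at least 80%, which is inferred from Table 2.

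The 42-month maximum contradicts sections 8 and 8.10. Under uniform accrual the effect is 2.5 to 2.7 expected events and at most about 0.6 points of power.

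The printed Table 1 values are correct for the inputs stated beside them. Nothing here bears on the choice of 500 patients or on the decision to stop, which the SAP addendum letter attributes to the low chance of a significant benefit.

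**What to change.** Change the Table 1 footnote to a 36-month maximum and rerun the table in the original software; the 36-month column above shows what to expect, and the method used should be named.

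State that adequate means at least 80%, and replace the exception with one that names each control rate, along these lines: *power is at least 80% except for reductions below about 31% when the 12-month standard-of-care rate is 24%, or below about 27% when it is 30%.* For completeness, add that the corresponding limit at a 36% rate is about 25%; without it, the sentence would again suggest that no limit applies there.

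The cost is one sentence, one footnote and a rerun of nine rows. The stated power becomes slightly less favourable. Sample size, endpoints and conduct do not change.

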11.4 Analysis of Secondary Endpoints

The analyses for the time-to-event secondary endpoints will be similar to those outlined for the primary endpoint using the time from randomization through the first occurrence of any component of a specific secondary endpoint (or censoring) as the response variable, and

CleanUP-IPF Protocol Amendment 2 Version Date: March 2, 2018

assessing group differences using the Cox proportional hazards model. Analyses of continuous secondary outcome variables will rely on a repeated measures approach, using mixed models and incorporating all available assessments. The analyses of all study endpoints will be detailed in the Statistical Analysis plan.

12. DATA MANAGEMENT PROCEDURES

12.1 Overview of Data Management

The DCRI will have primary responsibility for data management, including the development of data collection systems, data monitoring processes, and data storage and back up. State-of-the-art technology will be used for the management of the network's data.

12.2 Design and Development

The DCC will be responsible for development of the electronic case report forms (eCRFs), development and validation of the clinical study database, ensuring data integrity, and training clinical center staff on applicable data management procedures. A web-based distributed data entry model will be implemented. This system will be developed to ensure that guidelines and regulations surrounding the use of computerized systems used in clinical trials are upheld.

12.3 Data Collection Forms

The data collection process consists of direct data entry at the study clinical centers into the IBM Clinical Development study database. Data entry should be completed according to the instructions provided and project specific training. The investigator is responsible for maintaining accurate, complete and up-to-date records, and for ensuring the completion of the data collection forms for each research participant.

12.4 Data Acquisition and Entry

Data entry into eCRFs shall be performed by authorized individuals. Selected eCRFs may also require the investigator's written signature or electronic signature, as appropriate. Electronic CRFs will be monitored for completeness, accuracy, and attention to detail during the study.

12.5 Data Editing

Completed data will be entered into the IBM Clinical Development system. If incomplete or inaccurate data are found, a data clarification request will be generated and distributed to clinical centers for a response. Clinical centers will resolve data inconsistencies and errors and enter all corrections and changes into data management system and will adhere to the data entry and query response timelines specified by the CleanUP-IPF PLG.

12.6 Data Security

Access to databases will be controlled centrally by the DCRI through user passwords linked to appropriate privileges. This protects the data from unauthorized changes and inadvertent loss

or damage. Database and web servers will be secured by a firewall and through controlled physical access. Database back up will be performed daily using standard procedures in place at the DCRI. All disk drives that provide network services, and all user computers, will be protected using virus-scanning software.

13. STUDY ADMINISTRATION

13.1 Data and Safety Monitoring Board

A DSMB will be appointed by the NHLBI for this trial. It will include individuals with pertinent expertise in IPF and clinical trials. The DSMB will advise the Steering Committee regarding the continuing safety of current participants and those yet to be recruited. It is anticipated that the DSMB will meet approximately 2 times per year to review safety and overall study progress.

